6.7.1.2 Handling of additional treatment

Not applicable.

6.7.2 Instruction for prescribing and taking study treatment

All kits of study treatment assigned by the IRT will be recorded in the IRT system.

Study treatment (iscalimab 600 mg and 300 mg) will be administered s.c. by the participant, caregiver or site staff. The PFS will be provided by the site staff to the participant, who will self-administer the injections at the specified study time point. Participants will be instructed in detail how to self-administer the s.c. injection using the PFS. Site staff will administer the injection to those participants who are not able or unwilling to self-administer the PFS injection. Detailed instructions on the self-administration of the study treatment will be described in the IFU and provided to each participant. It shall be recorded on the corresponding eCRF(s) whether the participant self-administered the PFS or whether site staff or caregiver administered the PFS and whether it was administered at home or at the site.

Iscalimab 600 mg s.c. Q2W

- Iscalimab loading doses will be 600 mg s.c. (2 injections of 300 mg/2 mL) on Week 60E1 (Day 421), Week 61 (Day 428) and Week 62 (Day 435)
- From Week 62 the participant will receive 600 mg s.c. Q2W iscalimab until Week 106 (last dose)

Iscalimab 300 mg s.c. Q2W

- Iscalimab loading doses will be 600 mg s.c. (2 injections of 300 mg/2 mL) on Week 60E1 (Day 421), 300 mg s.c. (1 injection of 300mg/2 mL and 1 injection of 2 mL of the placebo) on Week 61 (Day 428) and 300 mg s.c. Week 62 (Day 435)
- From Week 62 the participant will receive 300 mg s.c. Q2W iscalimab until Week 106 (last dose)

The first study treatment administration will occur at Week 60E1 after the inclusion/exclusion criteria have been confirmed, all study scheduled assessments have been performed and the scheduled blood samples have been drawn. For the loading doses on Week 60E1 (Day 421), Week 61 (Day 428) and Week 62 (Day 435), all injections will be self-administered by the participant at the study site under the supervision of a site staff member after the study assessments for the visit have been completed. Participants will be required to attend the study site for the Week 64 visit and starting at Week 66, the participants will be allowed to self-administer the study medication at home on an alternating basis through to Week 106 or continue to present at the study site for injection administrations, based on the participant's preference and the investigator's judgment.

The trial-related safety and efficacy procedures will be conducted as indicated in [Table 8-1](#). While at the site visits, participants will be asked to refer to the IFU and to proceed with self-injection. At study visits requiring pre-dose blood samples, the participant will self-administer study treatment only after the blood samples have been collected.

For each study visit at the site, all study assessments including completion of Patient Reported Outcomes (PROs) should be completed prior to the self-administration of the study treatment.

All dosages prescribed and dispensed to the participants and all dose changes during the study must be recorded on the Dosage Administration Record CRF. Immediately before dispensing the package to the participant, site staff will detach the outer part of the label from the packaging and affix it to the source document (Drug Label Form) for that participant's unique participant number.

The investigator should promote compliance by instructing the participant to take the study treatment exactly as prescribed and by stating that compliance is necessary for the participant's safety and the validity of the study. The participant should be instructed to contact the Investigator if he/she is unable for any reason to take the study treatment as prescribed.

Administration

Single syringes will be packed in individual boxes. The site and participant should refer to the IFU for storage and handling instructions. Each injection should be administered into an appropriate injection site of the body (thighs, arms, or abdomen). Each new injection should be administered at the same site on opposite sides of the body or given on two different body sites. If the participant chooses the abdomen, a 2-inch area around the navel should be avoided. Investigational drug should not be injected into areas where the skin is tender, bruised, red, or hard or where participant has scars or stretch marks. Injection sites should be alternated to reduce the risk of reaction. Used safety syringes should be disposed immediately after use in a sharps container or according to the regulatory needs to the respective countries.

Home administration

Participants (or caregivers) will be allowed to self-administer the PFS at home when they are not visiting the site for any other trial-related procedures. Participants will be allowed to self-administer the PFS at home (starting at Week 66) only if they have exhibited correct use for self-administering the PFS at the site during the first 4 visits for treatment during the extension study. At such time points, if requested by the participant, a caregiver would be allowed to administer the study medication. Optional site visits have been included in the assessment table between the visits at which trial-related procedures are not to be conducted at the site. Participants will be allowed to self-administer the PFS at home or to visit the site during the optional visits to self-administer the PFS under the supervision of the site staff. If the participant is not able or not confident to self-administer the PFS, he/she should visit the site at every optional site visit (e.g., every 4 weeks) during the treatment period and the site staff will administer the PFS.

Prior to self-administration at home, participants should contact the investigator/site staff in the case they are experiencing any AE/SAEs or have any concerns or there have been changes to the ongoing concomitant medications.

7 Informed consent procedures

The following informed consents are included in this study:

1. Main study consent, which also includes a subsection that requires a separate signature for the optional consent for digital assessments and optional consent for digital injection care management device.

2. As applicable, Pregnancy Outcomes Reporting Consent for female subjects who took study treatment.

Eligible participants may only be included in the study after providing (witnessed, where required by law or regulation), IRB/IEC-approved informed consent.

If applicable, in cases where the participant's representative(s) gives consent (if allowed according to local requirements), the participant must be informed about the study to the extent possible given his/her understanding. If the participant is capable of doing so, he/she must indicate agreement by personally signing and dating the written informed consent document.

Informed consent must be obtained before conducting any study-specific procedures (e.g. all of the procedures described in the protocol). The process of obtaining informed consent must be documented in the participant source documents.

Novartis will provide to investigators in a separate document a proposed informed consent form that complies with the ICH GCP guidelines and regulatory requirements and is considered appropriate for this study. Any changes to the proposed consent form suggested by the investigator must be agreed by Novartis before submission to the IRB/IEC.

Information about common side effects already known about the investigational drug can be found in the IB. This information will be included in the participant informed consent and should be discussed with the participant during the study as needed. Any new information regarding the safety profile of the investigational drug that is identified between IB updates will be communicated as appropriate, for example, via an investigator notification or an aggregate safety finding. New information might require an update to the informed consent and then must be discussed with the participant.

Women of child bearing potential must be informed that taking the study treatment may involve unknown risks to the fetus if pregnancy were to occur during the study and agree that in order to participate in the study they must adhere to the contraception requirements.

[REDACTED]

[REDACTED]

[REDACTED]

A copy of the approved version of all consent forms must be provided to Novartis after IRB/IEC approval.

Participants might be asked to complete an optional questionnaire to provide feedback on their clinical trial experience.

8 Visit schedule and assessments

The Assessment Schedule ([Table 8-1](#)) lists all of the assessments when they are performed. All data obtained from these assessments must be supported in the participant's source documentation.

Participants should be seen for all visits/assessments as outlined in the assessment schedule ([Table 8-1](#)) or as close to the designated day/time as possible.

Every efforts should be made to adhere to the weekly dosing schedule (loading doses) and the bi-weekly maintenance dosing regimen in both arms in this trial.

Visits can be performed with the following time windows:

Treatment Period

- +/- 1 calendar day: from Week 60E1 (Day 421) to Week 61 (Day 428)
- +/- 2 calendar days: from Week 62 (Day 435) to Week 66 (Day 463)
- +/- 5 calendar days: from Week 68 (Day 477) to Week 108 (Day 757)

Follow-up Period

+/- 5 calendar days from Week 112 (Day 785) to Week 120 (Day 841)

Note: All efforts need to be made to maintain the actual duration of 48-week study treatment period. Therefore, a study visit subsequent to a visit, which has been delayed or brought forward needs to be planned as per original visit schedule.

Missed or rescheduled visits should not lead to automatic discontinuation. Participants who prematurely discontinue the study for any reason should be scheduled for a visit as soon as possible, at which time all of the assessments listed for the final visit will be performed. At this final visit, all dispensed investigational product should be reconciled, and the adverse event and concomitant medications recorded on the CRF.

As per [Section 4.6](#), during a Public Health emergency as declared by Local or Regional authorities i.e. pandemic, epidemic or natural disaster that limits or prevents on-site study visits, alternative methods of providing continuing care may be implemented by the investigator as the situation dictates. If allowed by local Health Authority and depending on operational capabilities, phone calls, virtual contacts (e.g. tele consult) or visits by site staff/ home nursing staff to the participant's home, can replace on-site study visits, for the duration of the disruption until it is safe for the participant to visit the site again.

Period	Extension-Treatment						Post-Treatment Follow-Up		
	Visit Name	Wk 98	Wk 100	Wk 102	Wk 104	Wk 106	Wk 108/TD ¹⁹	Wk 112	Wk 120/EOS ²⁰
Days	687	701	715	729	743	757	785	841	
Weeks	98	100	102	104	106	108	112	120	
Optional site visit ²	X		X		X				
Informed consent									
Inclusion / Exclusion criteria									
Contact IRT		X		X					
Study drug administration	X	X	X	X	X ²¹				
Demography									
Smoking history									
Medical history/current medical conditions									
Prior therapy for Sjögren's Syndrome									
Adverse Events ⁵	X	X	X	X	X	X	X	X	
Concomitant medications	X	X	X	X	X	X	X	X	
Physical Examination		S ⁷		S ⁷		S ⁷	S ⁷	S ⁷	
Vital signs and body measurements		X		X		X	X	X	
Electrocardiogram (ECG)						X			
Hepatitis and CMV monitoring (local) ⁹						S ⁷		S ⁷	
Hematology		X		X		X	X	X	
Clinical Chemistry		X		X		X	X	X	
Coagulation Panel ¹⁰						X			
Immunology		X				X	X	X	
Cryoglobulins ¹¹						X		X	
Pregnancy test ¹²		X		X		X	X	X	

Period	Extension-Treatment						Post-Treatment Follow-Up	
Visit Name	Wk 98	Wk 100	Wk 102	Wk 104	Wk 106	Wk 108/TD ¹⁹	Wk 112	Wk 120/EOS ²⁰
Days	687	701	715	729	743	757	785	841
Weeks	98	100	102	104	106	108	112	120

^X Assessment to be recorded in the clinical database or received electronically from a vendor

¹ Corresponds to the Week 60 visit of the core study. Assessments carried out as part of Week 60 as per core study protocol should be used for Week 60E1 of the extension study.

² Optional site visits - Week 66, 70, 74, 78, 82, 86, 90, 94, 98, 102, 106. Participants who are unable to self-administer the PFS injections at home will visit the site and site staff will supervise self-administration or administer the PFS injection for them. Other participants who can self-administer the PFS injection can do so at home at these optional visits.

³ Informed consent should be obtained before commencement of the Week 60 assessments of the core study.

⁴ Contact IRT for new treatment reassignment.

⁵ AEs/SAEs occurring after the participant has signed the informed consent must be captured on the appropriate eCRF page.

⁶ C - These assessments shall be conducted as part of the core study CCFZ533B2201 and will not be repeated in this extension study

⁷ S - Assessment to be recorded in the source documentation only

⁸ [REDACTED]

⁹ Local lab testing of CMV IgG, IgM and DNA (by PCR) must be performed every 3 months until end of study. Hepatitis B monitoring applicable to HBsAg (-) patients who were HBcAb (+) and HBV DNA (-) at screening during the core study. Local lab testing of HBsAg and HBV DNA must be performed every 3 months until end of study.

¹⁰ While on treatment, coagulation monitoring applies only to participants who have antiphospholipid antibodies (lupus anticoagulant, anti-cardiolipin antibodies) and/or who are on pre-existing antithrombotic therapy/prophylaxis, as reflected in the exclusion criteria of the TWINSS core study protocol.

¹¹ Analysis of cryoglobulins will be done only for participants who were positive at screening in the TWINSS core study.

¹² Urine pregnancy tests will be performed throughout the study

¹³ Blood sample is collected pre-dose.

¹⁴ [REDACTED]

¹⁵ [REDACTED]

¹⁶ Optional [REDACTED]

¹⁷ [REDACTED]

¹⁸ [REDACTED]

¹⁹ In case of premature discontinuation, participants will enter the follow-up after completing assessments for this visit.

²⁰ Mandatory to all participants, including those who have discontinued the study prematurely.

²¹ Week 106 is the last dose administration visit in the Treatment Period.

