4.1 Rationale for study design

This 1-year extension study will provide additional safety data for two doses of iscalimab (600 mg and 300 mg). This study will also provide continued administration of iscalimab for participants that as per Investigator may potentially derive clinical benefit after completing the core study. The extension study will provide additional key safety data for the two doses of iscalimab to better understand the overall safety of iscalimab and potentially inform study design elements of subsequent clinical studies (i.e., Phase III). The study will allow for the assessment of continued evaluation of efficacy and tolerability. Furthermore, digital data collected as part of the extension study will build on existing digital data for further validation.

A follow-up period of 12 weeks (14 weeks after the last dose) is required to reach sub-pharmacological exposures after completion of dosing and was estimated taking into consideration the non-linear pharmacokinetics (target-mediated disposition) of iscalimab - see [Section 4.2](#) below for detailed PK considerations.

The study is blinded until the final database lock of the core study to protect the integrity of the data in the ongoing core study. Participants can exit the study upon their own wish or based on advice of the Investigator at any time.

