As demonstrated in the PoC Study CCFZ533X2203 in pSS, a single s.c. dose of 600 mg iscalimab at Day 1 will deliver plasma concentrations generally above 40 µg/mL after 1 week. Subsequent weekly doses on Week 61 and 62 in Arms 1 and 2 are expected (i) to maintain CFZ533 plasma levels above 40 µg/mL, and (ii) to deliver iscalimab trough levels that are close to expected steady state conditions.

Further supportive arguments on the selected loading dosing regimen are provided in the Rationale for dose/regimen and duration of treatment of the TWINSS core study protocol (refer to Section 4 of the core study protocol).

Rationale for maintenance regimen

The maintenance regimen of 600 mg s.c. Q2W is expected to provide a median steady state trough plasma level at about 144 µg/mL (90% of the population within 282 - 46 µg/mL), in the upper range of trough levels observed in the PoC Study CCFZ533X2203-Cohort 2 (i.v. regimen; these concentrations were associated with clinical efficacy and suppression of a biologically relevant biomarker CXCL13 - a marker of germinal center activity).

The maintenance regimen of 300 mg s.c. Q2W is expected to deliver a median steady state trough plasma level at about 54 µg/mL (90% of the population within 125 - 0.1 µg/mL), with a reasonable chance to show efficacy in SjS.

The between subject variability in exposure within the two treatment arms (to a lesser extent in the 600 mg treatment arm) is likely to depend on the biology of CD40 in target tissues (expression level, turnover) and its potential modulation during the treatment period.

Rationale for the duration of the safety follow-up period (target engagement after the last dose)

Based on predicted median CFZ533 plasma concentration-time profile at 600 mg s.c. Q2W regimen, at about 14 weeks after the last dose, iscalimab plasma concentrations are expected to drop below 20 µg/mL with no expected pharmacodynamic activity in target tissues (e.g., germinal centers; data from non-human primates - please see current IB).

A 12-week follow-up period (14 weeks after the last dose) has been selected for the study and is justified to monitor for any related serious adverse events (SAE).

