6.5.3 Follow-up for toxicities

Participants whose treatment is interrupted or permanently discontinued due to an adverse event or clinically significant laboratory value, must be followed up at least once a week (or more frequently if required by institutional practices, or if clinically indicated) for 4 weeks, and subsequently at approximately 4-week intervals, until resolution or stabilization of the event, whichever comes first. Appropriate clinical experts should be consulted as deemed necessary. All participants must be followed up for adverse events and serious adverse events for 14 weeks following the last dose of CFZ533.

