3. its duration (start and end dates) or if the event is ongoing, an outcome of not recovered/not resolved must be reported
4. whether it constitutes a SAE (see [Section 10.1.2](#) for definition of SAE) and which seriousness criteria have been met
5. action taken regarding with study treatment

All adverse events must be treated appropriately. Action taken with the study medication must be recorded. It may include one or more of the following:

- Dose not changed
 - Dose Reduced/increased
 - Drug interrupted/withdrawn
6. Its outcome
 - not recovered/not resolved;
 - recovered/resolved;

- recovering/resolving,
- recovered/resolved with sequelae;
- condition deteriorated
- fatal, or unknown.

Conditions that were already present at the time of informed consent should be recorded in medical history of the subject.

Adverse events (including lab abnormalities that constitute AEs) should be described using a diagnosis whenever possible, rather than individual underlying signs and symptoms.

Adverse event monitoring should be continued for at least 14 weeks following the last dose of study treatment.

Once an adverse event is detected, it must be followed until its resolution or until it is judged to be permanent (e.g. continuing at the end of the study), and assessment must be made at each visit (or more frequently, if necessary) of any changes in severity, the suspected relationship to the interventions required to treat it, and the outcome.

Information about adverse drug reactions for the investigational drug can be found in the Investigator's Brochure (IB). This information will be included in the subject informed consent and should be discussed with the subject during the study as needed. Any new information regarding the safety profile of the medicinal product that is identified between IB updates will be communicated as appropriate, for example, via an Investigator Notification or an Aggregate Safety Finding. New information might require an update to the informed consent and has then to be discussed with the subject.

The investigator must also instruct each subject to report any new adverse event (beyond the protocol observation period) that the subject, or the subject's personal physician, believes might reasonably be related to study treatment. This information must be recorded in the investigator's source documents; however, if the AE meets the criteria of an SAE, it must be reported to Novartis.

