2.4 Safety analyses

All safety endpoints (i.e., adverse events, laboratory data, and vital signs in extension study will be summarized by treatment for all subjects of the safety set.

Adverse events (AEs)

All adverse events in extension study are summarized based on treatment emergent only. The definition for "treatment emergent" is as below:

TEAE includes all events up to the last dose date plus 14 weeks (98 days) or the end of the entire study period (including the safety follow-up period), whichever occurred earlier. A listing of all adverse events during the study will be produced, with those defined as TEAE for the study treatment period with "treatment emergent" flag displayed.

The number and percentage of patients with treatment emergent adverse event (TEAE) will be summarized for the following:

- by treatment, primary system organ class and preferred term
- by treatment, primary system organ class, preferred term and maximum severity
- by treatment, Standardized MedDRA Query (SMQ) and preferred term.

Summaries will also be provided for study treatment related adverse events, serious adverse events, treatment related serious adverse events, deaths, and adverse events leading to permanent discontinuation of study-drug.

If a particular AE 'severity' is missing, this variable will be listed as missing and treated as missing in summaries. If a subject reported more than one adverse event with the same preferred term, the adverse event with the greatest severity will be presented. If a subject reported more than one adverse event within the same primary system organ class, the subject will be counted only once with the greatest severity at the system organ class level, where applicable.

The most common adverse events reported ($\geq 5\%$ in any group for each preferred term in the table by PT or $\geq 5\%$ in any group for each SMQ table) will be presented in descending frequency according to its incidence in all subjects starting from the most common event.

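### The visit schedule does not guarantee the protocol's 14 weeks of follow-up after the last dose: a compliant completer can finish at 88 days, and the end-of-study date of early stoppers is not consistently defined

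*Protocol*

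**What the plan says.** The requirement runs from the last dose. Protocol Section 6.5.3: "All participants must be followed up for adverse events and serious adverse events for 14 weeks following the last dose of CFZ533". Section 10.1.1 makes it a minimum: "Adverse event monitoring should be continued for at least 14 weeks following the last dose of study treatment". Section 10.1.3 applies 14 weeks to the reporting of serious events.

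The schedule runs on visit days. Section 4.1 explains its length: "A follow-up period of 12 weeks (14 weeks after the last dose) is required to reach sub-pharmacological exposures". Section 4.2 makes the same equation: "A 12-week follow-up period (14 weeks after the last dose) has been selected for the study". A footnote to Table 8-1 fixes the last dose: "Week 106 is the last dose administration visit in the Treatment Period". Section 8 allows 5 days either side for Week 68 to Week 108, and for follow-up visits plus or minus "5 calendar days from Week 112 (Day 785) to Week 120 (Day 841"). The note after these windows keeps visits that follow a shifted visit on their planned dates.

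For early stoppers, Table 8-1 footnote 19 (attached to the Week 108/TD visit, TD being treatment discontinuation) says: "In case of premature discontinuation, participants will enter the follow-up after completing assessments for this visit". Footnote 20 makes Week 120/EOS mandatory for those who leave prematurely. Table 6-2 instead tells several groups who stop treatment to stay in the study and keep to the visit schedule.

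SAP Section 2.4 defines the window for treatment-emergent adverse events (TEAEs): "TEAE includes all events up to the last dose date plus 14 weeks (98 days) or the end of the entire study period", whichever comes first. SAP Section 2.1.1.5 derives a participant's study period from the end-of-period visit.

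**The concern.** Twelve weeks of follow-up equals 14 weeks after the last dose only if exactly 14 days separate the last dose from the start of follow-up. That holds on the nominal days for a completer. No passage makes it hold once visits move within their windows, or when treatment stops at an arbitrary point in the dosing cycle, and none sets a 98-day minimum between last dose and EOS.

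TEAEs are a primary endpoint. If a participant's EOS visit comes before day 98, the TEAE window closes with it. An event reported after that visit but by day 98 could appear in the listing of all adverse events without being counted as treatment-emergent. The EOS safety laboratory tests, pregnancy test, trough concentration and anti-drug antibody sample could also be taken before the 14 weeks that Section 4.1 gives for exposure to become sub-pharmacological.

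**Working it through.** **Inputs.** Week 106 (last dose) is Day 743, Week 108 is Day 757 and Week 120/EOS is Day 841 (Protocol Table 8-1). Week 106 and Week 120 each carry a window of 5 days either side (Section 8). The requirement is 14 × 7 = 98 days (Sections 6.5.3, 10.1.1 and 10.1.3).

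**The plan's own figure.** 841 − 743 = 98 days, or 14 weeks from the last dose. 841 − 757 = 84 days, or 12 weeks from Week 108. The SAP target days in Table 2-1 agree: 421 − 323 = 98 and 421 − 337 = 84. The stated equivalence is reproduced on nominal days.

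**Completers.** The interval is (841 + b) − (743 + a), where a and b are the deviations of the dose and of EOS, each from −5 to +5.
- Shortest: 836 − 748 = 88 days (12.6 weeks), 10 days short, or 10/98 = 10%.
- Longest: 846 − 738 = 108 days (15.4 weeks).
- The interval is under 98 whenever b is less than a. As an illustration only, if both deviations are independent and uniform over their 11 possible days, that is 55 of 121 combinations (45%), with a mean shortfall of 4 days among them. The documents give no distribution of visit dates.

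The Week 108 window plays no part, because EOS stays on its planned day.

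**Early stoppers, EOS kept at Day 841.** This is where Table 6-2 points for the groups it names. With a last dose at Week 104 (Day 729), the shortest interval is 836 − 734 = 102 days. Earlier last doses give more. There is no shortfall.

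**Early stoppers, follow-up read as 12 weeks from TD.** This is an assumption drawn from footnote 19. Let g be the days from last dose to TD, which the documents do not fix. EOS then falls g + 84 days after the last dose, 5 days either way.

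| g (days) | EOS, days after last dose | Against 98 |
|---|---|---|
| 0 | 79 to 89 | short by 9 to 19 |
| 3 | 82 to 92 | short by 6 to 16 |
| 8 | 87 to 97 | short by 1 to 11 |
| 9 | 88 to 98 | short except at the upper limit |
| 14 | 93 to 103 | nominally 98; up to 5 short |
| 18 | 97 to 107 | up to 1 short |
| 19 | 98 to 108 | never short |

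The latest in-window date reaches 98 when g + 89 ≥ 98, so g ≥ 9. The earliest reaches it when g + 79 ≥ 98, so g ≥ 19.

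**The case against.** The strongest reply is that collection of adverse events does not depend on the EOS visit. Sections 6.5.3, 10.1.1 and 10.1.3 bind sites to 14 weeks from the last dose in their own right. Section 9.1.1 allows events to be collected by telephone or email after discontinuation. Section 6.5.3 adds weekly contact for 4 weeks, then roughly 4-weekly contact until resolution or stabilization, for anyone stopped for an adverse event or significant laboratory value. This stands for collection. It does not settle how events are counted, because the SAP window closes at the earlier of the two dates. All events are listed, so what is at risk is the TEAE flag for those in the last days before day 98.

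It is also fair that 88 days needs opposite extremes of two windows, that the same windows allow 108, that Section 8 asks for visits as close to the planned day as possible, and that Section 4.2 speaks of about 14 weeks from a predicted median profile. A few days may matter little pharmacologically. Section 10.1.1 nonetheless says at least 14 weeks.

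A reader might infer more, in four ways that the documents do not support.
- That early stoppers as a class finish short. The result depends on g: 14 days gives the nominal 98, and 19 or more never falls short.
- That the protocol times EOS at 12 weeks from TD. Footnote 19 says only when follow-up is entered. Table 6-2, the Section 8 note and Section 9.1.1, which refers stoppers to the Assessment Schedule, can all point to the planned calendar.
- That a completer's EOS moves with the actual Week 108 visit, which would allow (752 + 84 − 5) − 748 = 83 days. The Section 8 note keeps it on Day 841.
- That those stopped for adverse events are the least observed. The extra contacts in Section 6.5.3 count against this.

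**Conclusion.** The point holds as an unreconciled conflict between the 14-week requirement and the visit schedule. For completers it follows directly from the stated windows and the Section 8 note: 88 to 108 days, so up to 10 days short. For early stoppers the size is not determined by the documents. There is no shortfall if EOS stays on Day 841. If follow-up is taken as 12 weeks from TD, EOS is always short for g up to 8, sometimes for g of 9 to 18, and never from 19, with the worst case 79 days at g = 0.

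The effect on the TEAE count rests on reading the end of the study period in SAP Section 2.4 as the participant's own end-of-period visit, as SAP Section 2.1.1.5 suggests. It is confined to events between an early EOS visit and day 98. How many participants or events that would involve cannot be estimated from the documents. The point is worth correcting because it touches a primary endpoint and costs little, but it does not show that safety is broadly under-ascertained.

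**What to change.** In the protocol, reconcile Sections 4.1, 4.2, 6.5.3, 8, 8.4.4 (the malignancy reporting period, which uses the last visit for some participants and 14 weeks for others), 10.1.1 and 10.1.3, Table 6-2, and footnotes 19 and 20 of Table 8-1. The timing of EOS relative to the actual last dose should be stated once, for completers and early stoppers alike, and should agree with the protocol's own 14-week requirement. How the visits are arranged to achieve this is for the sponsor to decide.

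In the SAP, align Sections 2.1.1.5 and 2.4 so that adverse events collected up to last dose + 98 days count as treatment-emergent even if the EOS visit came earlier. SAP Section 2.3.1 offers a precedent: it already measures exposure from the last dose because the visit windows and the end-of-treatment visit were judged a poor anchor.

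The cost is wording and one date derivation. The downside is a slightly later final visit for some participants.
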